7.2.4 Conventions for Missing Concomitant Medication Dates

Missing concomitant medication dates will not be imputed. Also see Section 7.7.

7.2.5 Pooling of Sites

The study team has reviewed the data in blinded fashion and decided to group sites into the following two groups: European sites and Non-European sites.

7.2.6 Protocol Deviations

Significant protocol deviations will be summarized, and all protocol deviations will be listed. A sperate listing will be created for protocol deviations due to COVID-19.

Important Protocol Deviations (IPD) are those, which have the potential to influence the outcome of the primary analysis and therefore, will be used to define the Per Protocol Set. Along with other protocol deviations, the IPD will include subjects that had < 75% compliance between visits for more than one occasion during the study, as assessed via the digital compliance technology. Those noncompliant subjects will be listed.

Additional important protocol deviations may also be identified prior to unblinding. If so, the additional important protocol deviations will be finalized and documented prior to database lock and used for deleting subjects from FAS set to define the Per Protocol Set. Important protocol deviations will also be summarized in a table by treatment groups and overall, and presented in the CSR. Also, important protocol deviations will be marked in the protocol deviation listing.

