7.3 Randomization Criteria

- 1. The subject must continue to meet all of the inclusion criteria and none of the exclusion criteria at the time of the baseline visit (Day 1; Visit 3).
- 2. The subject has completed the single-blind placebo run-in period and has met the study drug compliance criteria (75% to 125%) as assessed using the digital compliance technology. As an exception, subjects who are in a residential setting that incorporates directly observed medication administration who meet this criterion (but not via the digital compliance technology) may be eligible for randomization with site documentation and approval of the sponsor or designee.

NOTE: Before enrollment into the single-blind run-in period, the site must confirm that approval has been received from the study sponsor or designee, and from the central eligibility vendor. The sponsor or designee approval will also serve as approval of subject randomization provided that the subject meets the specified randomization criteria at the baseline visit.

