- 7. Unsatisfactory therapeutic response. The investigator has determined that the subject is not benefitting from study treatment and continued participation would pose an unacceptable risk to the subject.
- 8. Noncompliance with study drug during the double-blind treatment period. Noncompliance with study drug includes subjects who are <75% compliant between visits, as assessed via the digital compliance technology. As an exception, this criterion may be assessed via site-recorded compliance documentation for subjects who are in a residential setting that incorporates directly observed medication administration with approval of the sponsor or designee, as described for the placebo run-in period in Section 7.3. If these criteria for noncompliance are met on more than 1 occasion during the study, the subject will be considered significantly out of compliance and the site investigator will need to discuss the subject's continuation in the study with the sponsor or designee. Based upon the assessment of the investigator and sponsor or designee, an out-of-compliance subject may be withdrawn from the study.
- 9. Throughout the study, signs of suicidal risk will be assessed by C-SSRS and the investigator's clinical judgment. If the subject has a significant risk of suicide according to the investigator's clinical judgment, the subject will be withdrawn from the study.
- 10. Symptomatic deterioration: Any subject from the study who experiences a clinically significant psychotic episode, relapse in positive symptoms, or overall worsening of illness that poses an unacceptable risk to the subject based on the judgment of the investigator should be discontinued from study participation, and the event documented as an AE.
- 11. Other: The reason for discontinuation should be entered into the eCRF including unavoidable circumstances such as the COVID-19 pandemic.

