9.2 Monitoring Subject Treatment Compliance

A digital compliance technology will be implemented in this study. Further details regarding this technology is provided in the study reference manual. Subjects also will be required to bring study drug packaging to each clinic visit, regardless of whether the study drug packaging is empty.

All subjects should be reinstructed about the dosing requirement during study contacts. The authorized study personnel conducting the re-education must document the process in the subject source records.

Noncompliance with study drug includes subjects who are <75% compliant between visits (including noncompliance as assessed via the digital compliance technology). If these criteria for noncompliance are met on more than 1 occasion during the study, the subject will be considered significantly out of compliance and the site investigator will need to discuss the subject's continuation in the study with the sponsor (or designee). Based upon the assessment of the investigator and sponsor (or designee), an out-of-compliance subject may be withdrawn from the study. As an exception, subjects who are living in a residential setting that incorporates directly observed medication administration demonstrate ≥75% compliance (but not via the digital compliance technology) may be considered to be within these compliance requirements with study site documentation and approval of the sponsor or designee.

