7.0 METHODS OF ANALYSIS AND PRESENTATION

7.1 General Principles

Baseline values are defined as the last observed value before the first dose of study medication.

All statistical analyses will be conducted using SAS[®] Version 9.4, or higher, unless otherwise noted.

All confidence intervals, statistical tests, and resulting P-values will be reported as 2-sided and will be assessed at α =0.05 significance level unless otherwise stated. P-values will be rounded to 3 decimal places prior to assessment of statistical significance.

Means and medians will be presented to 1 more decimal place than the recorded data. The standard deviations (SDs) will be presented to 2 more decimal places than the recorded data. Confidence intervals about a parameter estimate will be presented using the same number of decimal places as the parameter estimate.

Where appropriate, variables will be summarized descriptively by study visit. For the categorical variables, the count and proportions of each possible value will be tabulated by treatment group. The denominator for the proportion will be based on the number of subjects who provided non-missing responses to the categorical variable. For continuous variables, the number of subjects with non-missing values, mean, median, SD, minimum, and maximum values will be tabulated.

Screen failure subjects will be grouped and listed at the end.

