7.3 Analysis Sets

The Full Analysis Set (FAS) will include all subjects who were randomized and received at least 1 dose of the study drug during the Double-Blind Treatment Period. In FAS summaries, subjects will be analyzed by the treatment to which they were randomized.

TAK-831-2002	Page 16 of 30
Statistical Analysis Plan Amendment No. 1	01 February 2021

The Per Protocol Set (PPS) will include all subjects in the FAS excluding those who had important protocol deviations.

The Safety Analysis Set will include all randomized subjects who received at least 1 dose of double-blind study drug. In safety summaries, subjects will be analyzed according to the treatment they received.

The PK Analysis Set will include all randomized subjects who received at least 1 dose of doubleblind study drug and who have any available TAK-831 plasma concentration data.

The PD Analysis Set will consist of all subjects who received at least 1 dose of study drug and have at least 1 postdose PD (plasma D-serine and L-serine) measurement.

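### SAP 7.2.6 scores the compliance deviation by the digital technology alone and omits the protocol's site-record exception for approved residential subjects, so compliant subjects can be dropped from the supportive Per Protocol Set

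*SAP*

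**What the plan says.** SAP 7.2.6 includes among the important protocol deviations "subjects that had < 75% compliance between visits for more than one occasion during the study, as assessed via the digital compliance technology". It adds that "Those noncompliant subjects will be listed", and it plans a table of important deviations by treatment group and a mark in the deviation listing. SAP 7.3 then states: "The Per Protocol Set (PPS) will include all subjects in the FAS excluding those who had important protocol deviations". SAP 7.9.1 repeats the primary MMRM on the PPS as a supportive analysis. SAP 7.14 records that this analysis was added because of the possible impact of noncompliant subjects.

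Protocol 7.6, item 8, sets the same threshold and occasion rule, with the digital technology as the main method, but it makes an exception: "this criterion may be assessed via site-recorded compliance documentation for subjects who are in a residential setting". The setting must be one where medication intake is directly observed, and the sponsor or designee must agree. Protocol 9.2 repeats this for residential subjects who reach at least 75% by non-digital means; they "may be considered to be within these compliance requirements with study site documentation and approval of the sponsor or designee". Protocol 7.3 has the parallel provision at entry, for residential subjects "who meet this criterion (but not via the digital compliance technology) may be eligible for randomization", so such subjects can be in the Full Analysis Set (FAS).

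No section of the SAP mentions residential subjects or site-recorded compliance.

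**The concern.** The SAP takes over the protocol's noncompliance test, both the threshold and the number of occasions, but leaves out the exception attached to it. The two documents can then classify the same subject differently. The protocol treats an approved residential subject with good site-recorded compliance as compliant. The SAP, followed literally, makes that subject an important protocol deviator if the device missed enough doses.

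The PPS analysis exists to show what noncompliance does to the primary result, so its definition of noncompliance should not sweep in subjects whose intake was directly observed and adequate. Three outputs are exposed: the PPS itself, the important-deviation table in the study report and the noncompliance listing.

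**Working it through.** **1. The rules side by side**

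| Element | Protocol 7.6 (item 8) and 9.2 | SAP 7.2.6 |
|---|---|---|
| Threshold | below 75% between visits | below 75% between visits |
| Occasions | more than one | more than one |
| Main method | digital technology | digital technology |
| Approved residential subject, observed dosing | site record may be used | no provision |
| Consequence | continuation discussed; withdrawal possible | important deviation; removed from PPS |

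Only the fourth row differs in how the test is scored.

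**2. One subject followed through.** Take an approved residential subject whose doses are all observed and documented by the site. The nearest scoring formula is the digital one in SAP 7.8: tablets recorded as taken, divided by 5 times the number of dosing days. SAP 7.8 states it for the whole dosing period, so applying it between visits is my assumption. From Day 28 to Day 42 the denominator is 5 × 14 = 70 tablets. If the device records 50 of them, the score is 50/70 = 71.4%. If the same happens from Day 42 to Day 56, there are two occasions below 75%. The site record shows 100% in both intervals. The protocol exception classes this subject as compliant. SAP 7.2.6 lists the subject as noncompliant and SAP 7.3 removes the subject from the PPS.

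**3. Is there a step that reverses this?**
- SAP 7.2.6 says "Additional important protocol deviations may also be identified prior to unblinding". That clause serves to remove further subjects from the FAS. It adds exclusions and cannot restore a subject.
- SAP 7.8 has a second compliance measure, from returned tablets. It is a whole-period summary, is not linked to the deviation rule and is not the site's observed-dosing record.
- Protocol 13.1 plans a blinded review that includes subject evaluability. It might catch individual cases, but no rule directs it to set aside a digital deviation.

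**4. Size.** The documents give neither the number of approved residential subjects nor their device capture. I assume k = 0 to 3 such subjects wrongly removed from one TAK-831 arm, planned arm sizes of 52 per TAK-831 dose and 78 on placebo, equal variances and no other exclusions.

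SE ratio = sqrt(1/(52 − k) + 1/78) / sqrt(1/52 + 1/78)

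- k = 0: 1.000
- k = 1: sqrt(1/51 + 1/78) / sqrt(1/52 + 1/78) = 1.006 (1/52 = 1.9% of the arm)
- k = 2: sqrt(1/50 + 1/78) / sqrt(1/52 + 1/78) = 1.012
- k = 3: sqrt(1/49 + 1/78) / sqrt(1/52 + 1/78) = 1.018 (3/52 = 5.8% of the arm)

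If the subjects were on placebo, the ratio is sqrt(1/52 + 1/(78 − k)) / sqrt(1/52 + 1/78): 1.003 for k = 1 and 1.008 for k = 3.

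**5. The plan's own figure.** The stated power of at least 82% does not depend on the PPS. It reproduces from 0.85 × 52 = 44.2 and 0.85 × 78 = 66.3 completers, effect size 0.4 and one-sided 0.05 per dose at Holm's first step. The noncentrality is 0.4 / sqrt(1/44.2 + 1/66.3) = 2.06, which gives 66.1% power per dose. With correlation 0.4 from the shared placebo arm, power for at least one dose is 82.8%. The omission in SAP 7.2.6 does not alter this.

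**The case against.** The best defence is that these are different rules for different purposes. Protocol 7.6 and 9.2 govern whether a subject's continuation is discussed; Protocol 13.1.1 defines no Per Protocol Set, so no protocol definition of that set is contradicted. The exception is also discretionary: site records may be used, with approval. SAP 7.8 names the digital technology as the primary compliance method, and one uniform measure for a supportive set is a defensible choice. All of that is fair. However, the SAP copies the protocol's test and attaches the label of important protocol deviation to it. A subject judged compliant under an approved protocol provision should not carry that label without explanation, and the SAP does not say that digital-only scoring was chosen deliberately.

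It can also be said that the issue may affect nobody. That stands. Appendix A schedules digital compliance training at Day -14 with no residential exemption, so low device capture cannot be presumed.

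A reader might go further and infer the opposite error as well: that a subject with no device record has no digital value, and so stays in the PPS even when the site record shows repeated noncompliance. The text that could suggest this is SAP 7.1: "The denominator for the proportion will be based on the number of subjects who provided non-missing responses to the categorical variable". The documents do not support that reading. SAP 7.1 concerns denominators for tabulated proportions, not the classification of deviations. The SAP 7.8 formula counts tablets recorded as taken, so unrecorded tablets lower compliance rather than make it missing. Any such subject could in any case be removed under the additional-deviations clause.

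**Conclusion.** The point holds in one direction only. As written, SAP 7.2.6 can classify an approved, adequately compliant residential subject as an important deviator and remove that subject from the PPS, and no stated step reverses it. This requires that such subjects exist and that their device capture falls below 75% on more than one occasion; the documents establish neither.

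Severity is low. Under the assumed range, the loss of precision in one supportive comparison runs from nothing to 1.8%. A reader might infer that the primary result is at risk. It is not: the primary MMRM uses the FAS, and the Holm procedure is unaffected. Nor are the SAP 7.8 compliance summaries wrong, since each is labelled by its method. What remains is a mismatch between the SAP's deviation rule and the protocol criterion it repeats, worth correcting because the correction is cheap and the PPS was added specifically to address noncompliance.

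**What to change.** Before unblinding, extend the compliance item in SAP 7.2.6. After its reference to the digital technology, add: or, for subjects approved under the residential exception in Protocol 7.6 (item 8) and 9.2, via the site-recorded compliance documentation. Flag those subjects in the listing. If digital-only scoring is in fact intended for the PPS, say so and give the reason.

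The cost is one clause, one flag and a small amount of work to bring the site records into the analysis data. The documents do not say whether those records are held in the eCRF, so that work cannot be sized exactly. The change applies a criterion the protocol already contains and adds no new clinical rule.

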7.3 Analysis Sets

The Full Analysis Set (FAS) will include all subjects who were randomized and received at least 1 dose of the study drug during the Double-Blind Treatment Period. In FAS summaries, subjects will be analyzed by the treatment to which they were randomized.

TAK-831-2002	Page 16 of 30
Statistical Analysis Plan Amendment No. 1	01 February 2021

The Per Protocol Set (PPS) will include all subjects in the FAS excluding those who had important protocol deviations.

The Safety Analysis Set will include all randomized subjects who received at least 1 dose of double-blind study drug. In safety summaries, subjects will be analyzed according to the treatment they received.

The PK Analysis Set will include all randomized subjects who received at least 1 dose of doubleblind study drug and who have any available TAK-831 plasma concentration data.

The PD Analysis Set will consist of all subjects who received at least 1 dose of study drug and have at least 1 postdose PD (plasma D-serine and L-serine) measurement.

7.4 Disposition of Subjects

Disposition of all screened subjects (denominator) will be tabulated (count and percent); there will be no inferential analysis of subject disposition data.

Summaries will be presented by treatment arm, TAK-831 overall and overall.

Disposition of all randomized subjects will be tabulated:

- All subjects received at least one dose of study drug (denominator).
- Subjects who completed the study.
- Subjects who prematurely discontinued study treatment.
- Subjects who prematurely discontinued study.

Primary reasons for discontinuation of study treatment or study will be entered on the electronic case report form (eCRF), will be tabulated. Reasons for premature discontinuation of study an and/or study treatment include death, adverse event, protocol deviation, lost to follow-up, withdrawal by subject, study termination by sponsor, pregnancy, lack of efficacy, noncompliance with study drug during the double-blind period, significant risk of suicide, and other. The date of first dose, date of last dose, duration of treatment and the reason for premature discontinuation of study drug/study visit will be presented for each subject in listings.

Disposition of screen failure subjects will be summarized descriptively. Primary reasons for failure will be summarized and will be presented in a data listing. Subjects who enter the Single-Blind Run-in Period but are not randomized, e.g., due to noncompliance with single-blind treatment, will be included as screen failures.

7.5 Demographic and Other Baseline Characteristics

Demographics and other Baseline characteristics including age, gender, race, body mass index, and medical history will be listed and summarized by treatment group and overall based on the FAS. Number of subjects by country and age category will be summarized.

Baseline values for efficacy assessments will also be summarized by treatment group and overall based on the FAS.

TAK-831-2002	Page 17 of 30
Statistical Analysis Plan Amendment No. 1	01 February 2021

7.6 Medical History and Concurrent Medical Conditions

Medical and psychiatric history to be obtained will include determining whether the subject has any significant conditions or diseases relevant to the condition/disease under study that stopped at or prior to informed consent, specifically psychiatric history, including number of previous hospitalizations (lifetime and in past year), duration of each hospitalization (in the past year), and age of initial diagnosis of schizophrenia. Ongoing medical or psychiatric conditions are considered concurrent medical conditions.

Medical history and concurrent medical conditions will be coded using the latest version of Medical Dictionary for Regulatory Activities (MedDRA, version 19.0) and will be summarized by treatment group and overall using System Organ Class (SOC) and MedDRA preferred term. The table will include number and percentages of subjects and will be sorted in alphabetical order by system organ class and preferred term. A subject will only be counted once within a particular class even if he/she has multiple conditions/symptoms. Summaries will be based on the safety analysis set.

All medical history and concurrent medical condition data will be presented in listings.

7.7 Medication History and Concomitant Medications

Medication history information to be obtained includes any medication relevant to eligibility criteria stopped at or within 30 days prior to signing of informed consent.

Concomitant medication is any drug given in addition to the study drug. If it is not possible to determine algorithmically from the reported data whether a medication was concomitant, it will be assumed to be concomitant.

Medication history and concomitant medications will be coded using the latest version of the World Health Organization (WHO, Version 01March2015) Drug Dictionary and summarized by giving the number and percentage of subjects by preferred term within each therapeutic class, with therapeutic class and medications in each class sorted in alphabetical order. The total number of subjects with medications in each selected therapeutic class will also be presented. If a subject reports taking 2 drugs belonging to the same class, he/she will only be counted once within that class. Summaries of medication history and concomitant medication will be based on the safety analysis set.

All prior and concomitant medications data will be presented in listings.

7.8 Study Drug Exposure and Compliance

Duration of exposure to double-blind study medication is defined as (date of last dose – date of first dose +1). It will be summarized as a continuous variable.

Study medication data will be collected by the study digital compliance technology and also by the number of tablets returned. The primary method of assessing compliance will be the digital technology.

The percentage of study drug compliance will be defined in two ways:

- Using the digital compliance technology, as {(number of tablets recorded as taken) / [5*(date of last dose date of first dose +1)]}x 100%,
- 2) Using number of returned tablets, {(number of tablets dispensed number of tablets returned) / [5*(date of last dose date of first dose +1)]} x 100%.

For each treatment group, study medication compliance will be summarized by compliance category (<75%, 75 to 125%, and >125%) and the number of subjects in each compliance category. Study medication compliance will also be summarized as a continuous variable using descriptive statistics (n, mean, SD, median, minimum, and maximum) for each treatment group.

All study drug administration and compliance data will also be summarized in a listing(s).

